6. RECRUITMENT MODALITIES

6.1 Scheduled (Elective) Cesarean Sections

Patients are identified at the preoperative consultation, generally conducted **48 to 72 hours** before the planned intervention. The investigator or a trained team member presents the study, answers questions, and provides the participant information document. Informed consent is obtained on the **morning of the intervention**, after verification of full understanding of the study modalities.

6.2 Cesarean Sections During Labor

Recruitment in the intrapartum context requires particular care. Only patients whose **clinical and emotional condition** permits serene and informed communication are approached. Patients in active distress, pain, or hemodynamically compromised are not solicited for enrollment.

7. RANDOMIZATION AND BLINDING

7.1 Randomization

Eligible participants are randomized in a **1:1 ratio** to receive either:

- **Group A:** Single-Layer Uterine Closure (SLC)
- **Group B:** Double-Layer Uterine Closure (DLC)

Randomization is performed using the **Clinical Trial Randomization Tool application**, generating a computer-based allocation sequence using **permuted blocks of variable sizes (4, 6, and 8)**, ensuring an unpredictable sequence and minimizing selection bias.

7.2 Allocation Timing and Procedure

The group allocation is revealed to the operating surgeon **on the day of the intervention only**, under the following sequential conditions:

1. **Verification of all eligibility criteria**

2. **Signed informed consent obtained**
3. **Fetal delivery and placental delivery completed**
4. **Immediately before performance of hysterorrhaphy**

This sequential allocation procedure ensures that randomization occurs as late as operationally feasible, maximizing allocation concealment and minimizing contamination.

7.3 Blinding

Actor	Blinding Status	Justification
Operating surgeon	Non-blinded	Must know the technique to be performed
Participants	Blinded	Not informed of the technique used
Ultrasonographers (evaluators)	Blinded	No access to allocation data
Principal Investigator	Non-blinded	Responsible for data centralization; holds both clinical and allocation data

8. INTERVENTIONS

8.1 Common Standardized Surgical Elements (Both Groups)

All cesarean sections are performed by **senior gynecologist-obstetricians or fourth- and fifth-year obstetric residents**, all experienced in both hysterorrhaphy techniques, according to a **strictly standardized operative protocol** from anesthesia to parietal closure. The only variable between groups is the hysterorrhaphy technique; all other operative steps are conducted uniformly.

Standard protocol elements include:

- **Anesthesia:** Spinal or general (recorded)
- **Skin incision:** Pfannenstiel or Joel-Cohen technique (recorded)
- **Fascial incision:** Transverse
- **Peritoneal entry:** Sharp or blunt (recorded)
- **Uterotomy:** Low transverse hysterotomy

- **Uterine exteriorization:** At surgeon's discretion (recorded)
- **Placental delivery:** Standardized technique
- **Peritoneal closure:** Not performed in either group
- **Fascial closure:** Continuous absorbable suture
- **Skin closure:** Subcuticular absorbable suture
- **Prophylactic antibiotics:** Standard institutional protocol

8.2 Group A — Single-Layer Closure (SLC)

The uterine incision is closed with a **single non-locking continuous suture (surjet continu non verrouillé)**, incorporating the **full thickness of the myometrium in one pass**, with **inclusion of the decidua**. Suture bites are of approximately 8–10 mm in depth and spacing, applied with appropriate tension to ensure hemostasis without tissue strangulation.

8.3 Group B — Double-Layer Closure (DLC)

The uterine incision is closed using **two successive non-locking continuous extra-mucosal sutures (surjets continus non verrouillés extra-muqueux)**, **excluding the decidua** in both layers:

- **First layer (deep):** Continuous non-locking suture incorporating the **inner half of the myometrium**, ensuring primary hemostasis and deep wall apposition
- **Second layer (superficial):** Continuous non-locking suture burying the first layer, incorporating the **outer half of the myometrium and the uterine serosa**

9. OUTCOME MEASURES

9.1 Primary Outcomes

1. **Residual Myometrial Thickness (RMT)** at the uterine scar site, measured by **transvaginal ultrasonography (TVUS)** at **6–8 weeks** and **6–7 months** postoperatively (millimeters)
2. **Prevalence of Cesarean Scar Defect (CSD)** at **6–8 weeks** and **6–7 months** postoperatively, defined per **European Niche Task Force criteria (Jordan et al., 2019)** as a triangular anechoic indentation **≥ 2 mm** of the anterior uterine wall at the scar site

9.2 Secondary Outcomes

Ultrasonographic outcomes:

- CSD morphological dimensions: depth, length, width (mm)
- CSD volume: estimated by ellipsoid formula — $V \text{ (mm}^3\text{)} = (\pi/6) \times \text{Length} \times \text{Width} \times \text{Depth}$
- **Adjacent Myometrial Thickness (AMT)**: measured 5–10 mm from the scar on both sides (mm)
- **Myometrial Ratio (RM)**: calculated as $\text{RM (\%)} = \text{RMT} / \text{AMT} \times 100$
- Uterine position (anteverted / retroverted)

Intraoperative outcomes:

- **Hysterorrhaphy duration** (minutes and seconds)
- **Total operative time** (minutes and seconds)
- **Visually Estimated Blood Loss (PSTEV)**: volume of bloody fluid in suction canister at end of surgery, minus estimated amniotic fluid volume (mL)
- **Calculated Total Blood Loss (PSTC)**:

$$PSTC(mL) = \frac{VST \times (Hct_{preop} - Hct_{postop})}{35} \times 100 + \text{Compensated losses}$$

Where: VST (Total Blood Volume) = Pre-pregnancy weight (kg) \times 65 \times 1.4;
Compensated losses = Number of packed red blood cell units transfused \times 500 mL; 35 = reference hematocrit of one packed RBC unit

- Number of **additional hemostatic sutures**
- **Intraoperative complications**: hysterotomy extension, ureteral injury, bladder injury, intestinal injury, hemorrhage requiring transfusion

Immediate postoperative outcomes:

- **Hemoglobin variation**: $\Delta\text{Hb (g/dL)} = \text{Hb preoperative} - \text{Hb at Day 1 postpartum}$
- **Transfusion requirement** (packed RBC units)
- **Early postoperative complications**: postpartum endometritis, surgical site infection, parietal hematoma, surgical revision, thromboembolic events

- **Hospital length of stay (days)**

Medium-term symptom outcomes (at 6–8 weeks and 6–7 months):

- Postmenstrual spotting (characteristic of CSD)
- Prolonged menstruation (> 7 days)
- Dysmenorrhea requiring medication
- Chronic pelvic pain (outside menstruation)
- Menometrorrhagia
- Dyspareunia

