- Independence of residuals (Durbin-Watson test)

- Absence of multicollinearity (Variance Inflation Factor < 5)
- Normality of residuals (Shapiro-Wilk on residuals)

Reported: Adjusted MD (β coefficient) with 95% CI, R^2 , adjusted R^2 , F-statistic, overall model p-value

SAP-4.3 CSD Prevalence — Analysis

Unadjusted:

- Chi-square test or Fisher's exact test (if expected cell count < 5)
- Relative Risk (RR) with 95% CI
- Absolute Risk Reduction (ARR) and Number Needed to Treat/Harm (NNT/NNH)

Adjusted:

- **Binary logistic regression** at 6–8 weeks and at 6–7 months
- Covariates: same set as RMT regression model
- Variables with $p < 0.20$ in univariate analysis AND a priori confounders (age, parity, BMI, indication) included
- Model fit: **Hosmer-Lemeshow test**
- Multicollinearity: **Variance Inflation Factors (VIF)**
- Discrimination: **Area Under the ROC Curve (AUC)**
- Results expressed as adjusted **Odds Ratios (OR)** with 95% CI

SAP-5. SECONDARY OUTCOME ANALYSES

SAP-5.1 Continuous Secondary Outcomes

- Unadjusted: t-test or Mann-Whitney U as appropriate
- Adjusted: Multiple linear regression (same covariate set)
- Results: Mean difference or median difference with 95% CI

SAP-5.2 Binary Secondary Outcomes (Complications, Transfusion)

- Unadjusted: Chi-square or Fisher's exact test
- Results: RR, ARR, NNT/NNH with 95% CI

SAP-5.3 CSD Morphological Dimensions

Analyzed within the **CSD-positive subgroup only**:

- Depth, length, width: Mann-Whitney U test
- **CSD Volume** (ellipsoid formula): Mann-Whitney U test

SAP-5.4 Repeated Measures — RMT at 6 Weeks and 6 Months

Method: Linear Mixed-Effects Model (LME)

Model structure:

- Fixed effects: treatment group, time point (6 weeks vs. 6 months), treatment × time interaction
- Random effect: participant-level intercept (accounts for within-subject correlation)
- Covariance structure: Unstructured (preferred); compound symmetry if convergence issues

Interpretation:

- Significant interaction ($p < 0.05$): treatment effect differs across time points
- Non-significant interaction: main effects interpreted independently

SAP-5.5 Symptom Outcomes (Ordinal / Binary)

- Binary symptoms (spotting, dyspareunia): Chi-square or Fisher's exact test; RR with 95% CI
- **Paired temporal evolution** (6 weeks → 6 months within each group): **McNemar's test**
- Adjusted: Binary logistic regression

SAP-5.6 Hemoglobin Variation and Blood Loss

- ΔHb : t-test or Mann-Whitney U; mean difference with 95% CI

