3.2 Secondary Objectives

1. To compare **intraoperative parameters** between groups, including hysterorrhaphy duration, total operative time, visually estimated blood loss (PSTEV), calculated total blood loss (PSTC), number of additional hemostatic sutures, and intraoperative complications.
2. To assess **immediate postoperative outcomes**, including hemoglobin variation (ΔHb), transfusion requirement, early postoperative complications (endometritis, wound infection, parietal hematoma, thromboembolic events, surgical revision), and hospital length of stay.
3. To evaluate **medium-term gynecological symptoms** potentially attributable to CSD at 6 weeks and 6 months, including postmenstrual spotting, prolonged menstruation (> 7 days), dysmenorrhea, chronic pelvic pain, menometrorrhagia, and dyspareunia.
4. To compare **CSD morphological characteristics** between groups, including defect depth, length, width, and estimated volume using the ellipsoid formula.
5. To assess the **adjacent myometrial thickness (AMT)** and the **myometrial ratio ($\text{RM} = \text{RMT}/\text{AMT} \times 100$)** at both evaluation time points.
6. To identify **clinical and surgical predictors** of CSD formation and reduced RMT.
7. To evaluate the **mediating role** of CSD at 6 weeks on RMT at 6 months.

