7.2 Intraoperative Continuous Outcomes

PSTC formula:

$$PSTC = \frac{VST \times (Hct_{preop} - Hct_{D1})}{35} \times 100 + (n_{RBC} \times 500)$$

VST = Pre-pregnancy weight \times 65 \times 1.4

Analysis: Mann-Whitney U; median difference with 95% CI

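### Hysterotomy extension is compared between arms as an outcome of closure, although the group is revealed only after the baby and placenta are delivered

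*Combined protocol and SAP*

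**What the plan says.** Protocol section 7.2 sets the order in which the group becomes known. Two of its conditions are "Fetal delivery and placental delivery completed" and "Immediately before performance of hysterorrhaphy". The stated purpose is that "This sequential allocation procedure ensures that randomization occurs as late as operationally feasible".

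Section 9.2 then lists the intraoperative complications that count as secondary outcomes: "hysterotomy extension, ureteral injury, bladder injury, intestinal injury, hemorrhage requiring transfusion". Nothing there limits them to events that begin after allocation. Secondary objective 1 (section 3.2) sets out what is compared for the operation itself: "between groups, including hysterorrhaphy duration, total operative time, visually estimated blood loss (PSTEV), calculated total blood loss (PSTC), number of additional hemostatic sutures". Complications during surgery are compared as well.

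For binary secondary outcomes, complications included, SAP-5.2 gives "Results: RR, ARR, NNT/NNH with 95% CI". The SAP inside the combined document does much the same in its section 7.3. SAP-9 puts secondary outcomes under a Holm-Bonferroni correction and calls them exploratory.

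Three other places bear on the point:
- SAP-3 does not list hysterotomy extension among the baseline variables, although it does list other features fixed early in the operation, such as anesthesia and skin incision type.
- Section 10 has a single intraoperative row covering randomization, blood loss and complications, with no timing relative to allocation.
- Sensitivity analysis SA-2 excludes women with an extension above 2 cm.

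**The concern.** A randomized comparison estimates an effect of closure technique only for events that the technique could influence. An extension of the hysterotomy at incision or at delivery of the baby has already happened when the surgeon learns the group. Its true between-arm effect is nil by design.

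If the plan is followed as written, whatever imbalance appears will still be tabulated with a relative risk and a number needed to treat or harm, next to events that closure might cause. Readers of a surgical trial take an NNH in a complication table as a consequence of the technique. The same applies to any bladder, ureteral or bowel injury that occurred before allocation. SA-2 adds an inconsistency: extension is an outcome in one analysis and a reason for exclusion in another.

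**Working it through.** **The plan's own figures.** The only calculated sample size is for RMT: 2 × (1.96 + 0.842)² × 3.5² / 1.3² = 113.8, so 114 per group, and 114 / 0.70 = 162.9, so 163. Both reproduce. The documents give no event rates or SDs for intraoperative outcomes, so the rates and SDs below are assumptions. The 192 per group is from section 11.

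**Order of events.** Under section 7.2 the order is: incision, fetal delivery, placental delivery, group revealed, hysterorrhaphy, end of surgery.

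| Outcome | Window | Can closure affect it? |
|---|---|---|
| Hysterotomy extension | Incision or delivery (inferred) | No |
| Organ injury, hemorrhage requiring transfusion | Either side of allocation; not stated | Only the part after allocation |
| PSTEV, total operative time | Whole operation | Yes, through the later part |
| Hysterorrhaphy duration, additional hemostatic sutures | Closure | Yes |

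**What chance alone would print for extension.** Assume a risk p of 5–10% in both arms. The SE of the difference is √[2p(1−p)/192].
- p = 0.05: √(0.095/192) = 0.0222, and 1/0.0222 = 45.
- p = 0.10: √(0.18/192) = 0.0306, and 1/0.0306 = 33.

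A chance difference at least this large arises in about 32% of trials (one SE, normal approximation). An NNT or NNH of about 45 to 33, or smaller, would therefore be unremarkable with no effect present.

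**Holm-Bonferroni.** The plan does not enumerate the family. If it held only the five listed complications, the threshold for the smallest p-value would be 0.05/5 = 0.010. Without extension it would be 0.05/4 = 0.0125. In a larger family the change is smaller.

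**Only if complications were pooled.** Assume closure-related risks q of 2% vs 5% (RR 2.50, difference 3.0 points) and a pre-allocation risk b in both arms. The pooled risk is 1 − (1−b)(1−q). Power uses a two-sided 5% normal test with SE = √{[p₁(1−p₁) + p₂(1−p₂)]/192}.

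| b | Risks | RR | Difference | 1/difference | Power |
|---|---|---|---|---|---|
| 0 | 2.0% vs 5.0% | 2.50 | 3.00 points | 33 | 36% |
| 5% | 6.9% vs 9.75% | 1.41 | 2.85 points | 35 | 17% |
| 10% | 11.8% vs 14.5% | 1.23 | 2.70 points | 37 | 12% |

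The ratio and the power fall markedly. The absolute difference hardly moves.

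**PSTEV.** Let pre-allocation loss have an assumed SD of 250 mL and closure-phase loss 150 mL, taken as independent. The total SD is √(250² + 150²) = 291.5 mL. The expected mean difference is unchanged, because pre-allocation loss is balanced by randomization. The standardized effect is multiplied by 150/291.5 = 0.51, and the sample for equal power by (291.5/150)² = 3.8 (2.0 if the two SDs are equal). Total operative time behaves in the same way.

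**The case against.** The strongest case against is that this is a small wording matter among exploratory secondary outcomes, and that wider claims built on it fail. Much of that stands.

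- A reader might infer that the whole safety comparison is diluted. That requires an any-complication endpoint. Section 9.2 lists five events and SAP-5.2 does not pool them. If each is analyzed alone, extension dilutes none of the others. Even when pooled, the ARR and NNH that SAP-5.2 also reports barely change.
- A reader might infer that blood loss and operative time are invalid or biased because they begin before allocation. They are not biased on that account: they lose precision. The plan already has closure-specific measures in hysterorrhaphy duration and additional hemostatic sutures.
- PSTEV is read when surgery ends, less an estimated amniotic fluid volume, and section 7.3 leaves the surgeon unblinded. That may suggest a biased estimate, but no section says who makes it or when. It is also a separate matter from allocation timing.
- The documents do not say when organ injuries occur. Some may arise during or after closure, so the whole list cannot be treated as pre-allocation.
- SA-2 shows that the authors recognize extension as a special case. It is a sensitivity analysis, however, and does not alter the comparison in SAP-5.2.
- Section 5.3 labels a corporeal hysterotomy a post-randomization event, which may suggest earlier randomization. Even if the sequence exists earlier, a group that has not been revealed cannot influence the hysterotomy. Sections 5.3 and 7.2 should be reconciled.

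None of this supplies a reason to report an NNT or NNH for extension.

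**Conclusion.** The point holds for hysterotomy extension, and for any organ injury shown to have occurred before allocation. As written, the plan would report a chance imbalance in extension as an effect of closure technique. At an assumed 5–10% risk, a one-SE imbalance corresponds to an NNT of about 45 to 33. The added null test in the Holm-Bonferroni family is a minor further cost. The fall in RR from 2.50 to 1.41 or 1.23 is conditional on a pooled endpoint that the plan does not define, and should not be read as an expected loss.

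The conclusion rests on two assumptions: that extensions arise at incision or delivery, which is inferred from the sequence in section 7.2, and that they are recorded alike in both arms. PSTEV and total operative time remain legitimate randomized outcomes. The primary RMT and CSD comparisons are untouched.

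**What to change.** - Add hysterotomy extension to the SAP-3 baseline variables and Table 1, and remove it from the SAP-5.2 comparison, including RR, ARR, NNT/NNH and the Holm-Bonferroni family. Make the matching change in protocol section 9.2 and in the SAP within the combined document.
- Treat in the same way any bladder, ureteral or intestinal injury that the operative notes show occurred before the group was revealed. Before unblinding, fix how injuries of unknown timing will be counted, and report their number.
- Keep PSTEV and total operative time as randomized outcomes, labelled as whole-operation measures that include the pre-allocation phase. Name hysterorrhaphy duration and additional hemostatic sutures as the closure-specific measures.
- State whether complications are analyzed singly or pooled.

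The cost is a few lines of text and a review of the operative notes for women with an organ injury. The downside is that timing may be missing for some of them. New data collection, such as a second canister reading when the group is revealed, is not available: section 4.3 ends recruitment on 31 December 2025 and the standalone SAP is dated 23 April 2026.

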10. DATA COLLECTION AND FOLLOW-UP SCHEDULE

Time Point	Assessment
Preoperative	Eligibility verification, informed consent, baseline NFS (CBC), demographics
Intraoperative	Randomization, surgical parameters, hysterorrhaphy duration, operative time, blood loss, complications
Postoperative Day 1	NFS (hemoglobin), vital signs, wound assessment
Discharge	Wound assessment, clinical evaluation, length of stay
6–8 Weeks postpartum	TVUS (RMT, CSD assessment), AMT, RM, clinical examination, standardized symptom questionnaire
6–7 Months postpartum	TVUS (RMT, CSD — PRIMARY ENDPOINT) , AMT, RM, CSD dimensions, volume, standardized symptom questionnaire

Ultrasonographic Examination Protocol

All TVUS examinations are performed:

- By a **dedicated, trained ultrasonographer per center, blinded to group allocation**
- Using **Samsung HS40 ultrasound system with EVN4-9 endovaginal probe (4–9 MHz)**
- With **standardized imaging parameters**

- With the **bladder empty**
- **Preferably in the follicular phase (Day 7–14 of the menstrual cycle)** to optimize defect visualization
- In the **mid-sagittal plane**: depth, length, and RMT measured; width measured in transverse plane
- **RMT measured perpendicular to the serosa at the thinnest point of the scar**

11. SAMPLE SIZE CALCULATION

The sample size was determined based on the primary outcome — **RMT at 6 months** — using the standard formula for comparison of two independent means:

$$n = \frac{2 \times (Z_{\alpha/2} + Z_{\beta})^2 \times \sigma^2}{\Delta^2}$$

Parameters:

- Two-sided significance level: $\alpha = 0.05$ ($Z_{\alpha/2} = 1.96$)
- Statistical power: 80% ($Z_{\beta} = 0.842$)
- Conservative standard deviation: **$\sigma = 3.5$ mm**
- Minimum clinically meaningful difference: **$\Delta = 1.3$ mm**

Base sample size: 114 participants per group

Adjustment for loss to follow-up:

Based on local postpartum follow-up data and published literature, a **30% loss to follow-up rate** was anticipated:

$$n_{adjusted} = \frac{114}{1 - 0.30} \approx 163 \text{ per group}$$

Total enrolled: 384 participants (192 per group)

12. ETHICAL CONSIDERATIONS

The trial is conducted in accordance with:

- The **Declaration of Helsinki** (2013 revision)

- **ICH Good Clinical Practice (GCP) Guidelines E6(R2)**
- Applicable Tunisian national regulatory requirements

Ethical approval was obtained from the **Institutional Review Board (IRB) / Ethics Committee of CHU Hédi Chaker, Sfax** prior to enrollment of the first participant. All protocol amendments are submitted for ethics review before implementation.

13. DATA MANAGEMENT AND CONFIDENTIALITY

- All data are recorded in a **standardized data collection form** at each stage: inclusion, intervention, hospital follow-up, and outpatient consultations
- Each participant is assigned a **unique identification number**; no identifying information appears in the analysis database
- The **principal investigator** is the sole person with simultaneous access to both participant clinical/epidemiological data and group allocation
- Ultrasonographers and data analysts have access only to anonymized data
- Source documents are retained for a minimum of **15 years** following study completion
- Data access is restricted to **authorized study personnel only**

14. DISSEMINATION POLICY

Results will be disseminated regardless of direction of findings through:

- Peer-reviewed scientific publications
- International obstetric and gynecological conferences
- ClinicalTrials.gov results posting within **12 months** of study completion

STATISTICAL ANALYSIS PLAN

Document Title: Statistical Analysis Plan — SLdl-HYS Trial (Standalone Version)

Full Study Title: Single-Layer Versus Double-Layer Uterine Closure (Hysterorrhaphy) After Primary Cesarean Section: Impact on Residual Myometrial Thickness and Cesarean Scar Defect Formation

Date of Finalization: January 2025 (*finalized prior to database lock and unblinding*)

Responsible Statistician: [[name], PhD/MSc Biostatistics, Affiliation]

Principal Investigator: [[name], CHU Hédi Chaker, Sfax, Tunisia]

